10.2.11 Adverse Event and Serious Adverse Event Reporting

All AEs should be recorded using acceptable diagnoses, if possible. If an AE has already been reported (by the investigator to the Sponsor/CRO) it is not necessary to report each individual sign and symptom of that AE as a separate AE. For example, if myocardial infarction is reported as an AE, there is no need to report elevated creatine kinase and abnormal ECG, or other related signs, symptoms, or laboratory values as separate AEs. However, if both occurred in isolation and myocardial infarction was not diagnosed, then each event would be reported as an AE.

The intensity of all AEs will be graded as mild, moderate, or severe using the following definitions:

Mild: Tolerable.

Moderate: Interferes with normal activity.

Severe: Incapacitating (causes inability to perform usual activity or work). The investigator will be instructed to closely monitor each patient who experiences an AE (whether ascribed to AdreView™ or not) until the outcome of the AE has been determined.

In addition to the investigator's own description of the AEs, each AE will be encoded by the Sponsor/CRO according to a well-recognised dictionary of medical codes (Medical Dictionary for Regulatory Activities [MedDRA]).

All serious and non-serious AEs must be followed for a final outcome until the end of the follow-up period. An outcome of "unknown" is not considered to be an acceptable final outcome. An outcome of "not yet resolved" is an acceptable final outcome for non-serious AEs at the end of a patient's participation in a study, and for SAEs at database lock.

SAEs must be notified to the Sponsor/CRO within 24 hours. Details regarding how to notify the Sponsor/CRO of SAEs and contact details for any protocol or safety-related questions will be provided in a separate document.

Patients enrolled at sites in the European Union will be provided with a Clinical Trial Participant card at the time of enrolment. This card will list contact details for the investigator and for GE Healthcare medical emergency cover services (Clinical Trial Emergency Contact Service [CTECS]). The CTECS provides 24 hour, 7 day a week emergency cover service for healthcare professionals to seek advice on study-related medical questions or problems should a medical emergency arise and the investigator is not available.

10.2.12 AdreView™-emergent Serious Adverse Event Reporting

Any AdreView™-emergent SAE must be forwarded immediately by the initial recipient at the Sponsor/CRO to the Global Pharmacovigilance mailbox:

[REDACTED]

10.2.13 Urgent Safety Measures

In accordance with the principles of GCP as laid out in ICH E6, the investigator(s) has/have primary responsibility for assuring patient safety throughout the performance of study procedures. An urgent safety measure is defined as any measure which an investigator may need to implement which is a deviation from, or a change in, the protocol to eliminate an immediate hazard(s) to study patients without prior IEC/IRB approval/favourable opinion.

The investigator may take appropriate urgent safety measures in order to protect the patients of a clinical study against any immediate hazards to their health or safety. However, the investigator must inform the Sponsor/CRO within 24 hours of having taken such measures.

The Sponsor in turn shall immediately, and in any event no later than 3 days from the date the measures are taken, give written notice to the licensing authority and the relevant IEC/IRB of the measures taken and the circumstances giving rise to those measures.

All urgent safety measures must be reported to the Sponsor/CRO using the SAE contact numbers listed in Section 10.2.11 within 24 hours of having to take such a measure(s). Such reports can be initiated by telephone but must be officially documented by the investigator (by email or fax) and must include details of what measures were taken and the circumstances giving rise to those measures.

10.2.14 Pregnancy Reporting

This process is aimed at ensuring the appropriate monitoring of the potential risk related to AdreView™ exposure of pregnant women and/or foetuses as well as the risks associated with exposure of a father, regarding congenital abnormalities or birth defects in their offspring. It also ensures compliance with applicable international and local regulations.

The requirements are applicable to all patients following exposure to AdreView™.

Female study patients: The study patient must be advised by the investigator to inform him/her immediately if she suspects she may be pregnant and believes conception occurred within 72 hours of AdreView™ administration.

Male study patients: The study patient must be advised by the investigator to inform him/her immediately if he suspects his partner became pregnant within 72 hours after AdreView™ administration.

When a study patient reports a pregnancy (post-AdreView™ administration) to the investigator, a pregnancy test should be arranged for the study patient (or their partner) by the investigator within 7 days of the pregnancy being reported.

The investigator must inform the Sponsor/CRO within 24 hours of receiving positive pregnancy test results using either a copy of the relevant eCRF page (demography or AE) or via email. The investigator should include an estimated date of conception when communicating with the Sponsor/CRO.

10.3 Appropriateness of Measurements

All assessments and measurements are appropriate and generally regarded as standard medical practice.

11 DATA HANDLING AND QUALITY ASSURANCE

11.1 Completing and Signing Case Report Forms

For eCRFs, data will be entered by trained site personnel with reasons given for any missing data. Any errors should be corrected within the electronic system. The audit trail will record all changes made, the date and time of the correction, and the person correcting the error. The appropriate electronic signature will be provided.

Any data recorded directly in the eCRF, for which no other written or electronic record will be maintained in the patient's medical record, will be considered source data and should be signed by the investigator(s) (e.g., results of physical examinations, vital signs testing, or the AdreView™ administration procedure).

11.2 Clinical Data Management

A CRO will be responsible for the processing and quality control of the data. Data management will also be carried out by a CRO. The handling of data, including data quality control, will comply with all applicable regulatory guidelines.

11.3 Archiving

All study documentation at the investigator site and Sponsor site will be archived in accordance with ICH E6- GCP, and the Sponsor/CRO's quality standards and SOPs.

Current EU Directive and ICH guidelines collectively require that essential clinical study documents (including eCRFs) other than the patient's medical files must be retained for the following time period:

- For at least 15 years after completion or discontinuation of the study,
- Or 2 years after the last approval of a marketing application in an ICH region and until there are no pending or contemplated marketing applications in an ICH region,
- Or at least 2 years have elapsed since the formal discontinuation of clinical development of the investigational product.

National guidelines and regulations in individual countries should be followed as appropriate.

12 STATISTICAL METHODS AND PLANNED ANALYSIS

The data will be analysed by a Sponsor-designated CRO. Any data analysis carried out independently by the investigator should be submitted to the Sponsor before publication or presentation.

Data from participating centres in this protocol will be combined so that an adequate number of patients will be available for analysis. The data will be summarised with respect to demographic and baseline characteristics, efficacy observations and measurements, and safety observations and measurements.

12.1 General Statistical Considerations

Tabulations of summary statistics, graphical presentations, and statistical analyses will be performed using SAS® software, Version 9.2 or higher. Descriptive statistics for continuous data in summary tables will include the number of patients in the analysis (n), mean, standard deviation (SD), median, and range (minimum, maximum). Descriptive statistics for categorical data in summary tables will include counts and percentages. For the AdreView™ and SoC groups, the baseline value will be the last observation obtained before randomisation. All data obtained on the eCRF and entered into the database will be provided in separate data listings showing individual patient values. All summary tables and data listings will be separated by enrolment groups. The planning and reporting of statistical analysis will be carried out as described in the CRO's SOPs governing clinical studies.

12.2 Populations for Analysis

A patient is defined as having been included into the study if he/she has met all inclusion criteria, none of the exclusion criteria, and has been assigned to 1 of the enrolment groups (the AdreView™ group or the SoC group). The primary efficacy population is defined as those patients who were randomised to the AdreView™ group or the SoC group.

All randomised patients will be analysed for efficacy in the group to which they were randomised.

The safety population is defined as all patients who were enrolled in the study. All patients will be analysed for safety in the enrolment group to which they were assigned.

12.2.1 Determination of Safety and Efficacy Population

The rules for determination of the efficacy populations (primary and secondary) and the safety population are given in Section 12.2 above. Protocol violations will play no part in patient inclusion in the efficacy or safety populations.

12.3 Patient Demographics/Other Baseline Characteristics

A table will be provided with the following information:

- Number of patients screened/enrolled.
- Number of patients included in the efficacy analysis.
- Number of patients included in the safety analysis.
- Number of patients withdrawn from the study and the reason for withdrawal.

Demographic information (age, height, weight, and body mass index [BMI]) will be summarised using descriptive statistics. Gender and race will be summarised by counts and percentages.

Medical histories will be summarised by counts and percentages. Prior and concurrent medications will be recorded and coded using a standard classification system and grouped by primary and secondary classes, if applicable.

12.4 Study Treatments

For each AdreView™ administration, the dose (MBq) and volume (mL) will be summarised.

12.5 Primary Analysis

12.5.1 Variable

The primary endpoint is all-cause mortality

12.5.2 Statistical Hypothesis, Model, and Method of Analysis

This is an event-driven study. The primary efficacy analysis will take place after 247 instances of the primary efficacy endpoint have accrued. The primary efficacy endpoint will be analysed for non-inferiority. If the upper bound of the confidence interval is less than 1, superiority will be claimed/ established.

The primary null hypothesis is: H_0 : hazard ratio (HR) (AdreView™ group / SoC) \geq HR_0 .

The primary alternative hypothesis is: H_a : HR (AdreView™ group / SoC) $<$ HR_0 .

For this study, HR_0 is chosen to be 1.20.

The primary efficacy analysis will be performed in the primary efficacy population using the Cox proportional hazards model stratified by enrolling centre, with method of treatment guidance (SoC vs AdreView™ group) as the only covariate.

This analysis will be performed at a 1-sided alpha value of 0.025.

12.5.3 Handling of Missing Values/Censoring/Discontinuations

No imputation will be performed for any of the efficacy endpoints.

12.5.4 Supportive Analyses

A sensitivity analysis on the primary efficacy analysis will be performed using the Cox proportional hazards model stratified by enrolling centre, with method of treatment guidance (AdreView™ group vs. SOC), LVEF, NYHA Classification, and BNP or NT proBNP as initial covariates. A stepwise regression with forward selection will be used to choose the final statistical model.

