10.2.1 Clinical Laboratory Evaluation

Clinical laboratory parameters assessed in this study are displayed in [Table 2](#).

Table 2 Clinical Laboratory Parameters

Serum Biochemistry	Haematology
Chloride	Haematocrit
Urea nitrogen	Haemoglobin
Creatinine	Platelet count
Bicarbonate	White blood cell (WBC) count
Sodium	Lymphocyte %
Potassium	
Glucose	Troponin
Alkaline phosphatase	ST2 and Gal 3 biomarkers (if available for on-site determination).
Aspartate transaminase	
Alanine transaminase	
Bilirubin (Total)	
Brain natriuretic peptide (BNP) or N-terminal pro b-type natriuretic peptide (NT proBNP)	

The signed and interpreted laboratory results will be kept together with the patient's eCRF (paper or electronic) as supplemental pages at the site.

Blood samples will be obtained for assessment of serum biochemistry and haematology at enrolment ([Table 1](#)). Samples will be analysed at the local laboratory (for parameters, see [Table 2](#)). All blood samples will be processed and handled per standard laboratory procedures.

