12.8 Sample Size Calculation

Assumptions:

The all-cause mortality rate that is expected in the study has been estimated using the all-cause mortality rate observed in Study GE-122-016 at 36 months (internal report). It is assumed:

	Patients with $25\% \leq \text{LVEF} \leq 30\%$		Patients with $30\% \leq \text{LVEF} \leq 35\%$	
	%	Mortality Rate	%	Mortality Rate
H/M ratio <1.6	79%	20.25%	75%	15.14%
H/M ratio ≥ 1.6	21%	9.72%	25%	4.68%

In addition, the following observations or assumptions were taken: the ratio of patients with $25\% \leq \text{LVEF} \leq 30\%$ vs $30\% \leq \text{LVEF} \leq 35\%$ is expected to be 1:4 to account for the prior enrollment of only patients with $30\% \leq \text{LVEF} \leq 35\%$; the hazard ratio of patients with ICD implantation vs with usual care in the existing practice is 0.9 [Køber et al. 2016]. Referring to existing practice, only 15% of patients with $25\% \leq \text{LVEF} \leq 35\%$ currently receive ICD. Accordingly, the number of patients who currently do not receive ICD but who will receive it according to protocol and the number of patients who currently receive ICD and who will not receive it according to protocol have been calculated. In addition, the all-cause mortality rate of patients currently not receiving ICD but who will receive according to protocol (85% of patients with H/M ratio <1.6 in the AdreView™ group) has been corrected to take into account the 31% reduction in all-cause mortality observed at 20 months in the MADIT II trial [Moss et al. 2012]. These assumptions led to a composite mortality rate of 11.34% in the AdreView™ group and 13.33% in the SoC group. The sample size is estimated with the hypothesis of not having a relative increase of mortality rate in excess of 20% and with the following assumptions:

- Alpha = 0.025, 1-sided.
- Statistical power = 80%.
- 1:1 randomisation to AdreView™ and SoC groups.
- $H_0: \text{HR} \geq \text{HR}_0$ vs $H_1: \text{HR} < \text{HR}_0$. $\text{HR}_0 = 1.20$.
- Assumed HR: 0.84.
- Accrual time: 18 months.
- The total study duration: 48 months.
- AdreView™ group survival rate at 36 months: 0.887.

Based on the above assumptions, the required total number of events will be 247, and the required total number of randomized patients will be 2001.

The planned study accrual will be at least 2354 patients screened in order to randomize at least 2001 patients in the study.

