12.9 Non-Inferiority Margin

The NI margin to be used for the analyses summarized in Sections 12.5.2 and 12.6.1 will be 1.20.

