5.4.2 Primary Efficacy Analysis

The primary endpoint is the hazard ratio of the all-cause mortality between the AdreView™ group and SoC. The primary efficacy endpoint will be analyzed for non-inferiority (NI) with the NI boundary equal to 1.2. If the upper bound of the confidence interval for the HR is less than 1, superiority will be claimed/ established.

The hypothesis testing for the primary objective is:

$$H_0: \text{hazard ratio (HR)} (\text{AdreView}^{\text{TM}} \text{ group} / \text{SoC}) \geq 1.2$$

$$H_a: \text{HR} (\text{AdreView}^{\text{TM}} \text{ group} / \text{SoC}) < 1.2$$

Cox proportional hazards model stratified by country, with study arm (AdreView™ group vs SoC) as the only covariate will be performed at a 1-sided alpha value of 0.025 for the primary endpoint.

Kaplan-Meier plot will be presented by method of treatment guidance. Patients who are still alive at the time of data base lock will be censored at the last known-alive date.

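### The one covariate-adjusted sensitivity analysis of mortality does not guarantee a treatment hazard ratio, and the SAP omits it without explanation

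*Protocol*

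**What the plan says.** Protocol 12.5.4 (repeated in the synopsis) describes one sensitivity analysis of the primary endpoint. It is a Cox model stratified by enrolling centre that names four terms as *initial covariates*: treatment guidance, LVEF, NYHA class, and BNP or NT-proBNP. The final model is then left to selection: "A stepwise regression with forward selection will be used to choose the final statistical model". The text does not say that treatment stays in the model, gives no p-value for entry or removal, and has no rule for combining the two natriuretic peptide assays. Protocol 10.2.1 lists the assays as alternatives, measured at local laboratories.

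The SAP's primary model is stratified by country, "with study arm (AdreView™ group vs SoC) as the only covariate will be performed". SAP 5.4.1 to 5.4.4 contain no sensitivity analysis and no covariate-adjusted efficacy model. The secondary Cox models follow the primary one, and the Cochran-Mantel-Haenszel tests are stratified by country only. SAP Section 1 says the document elaborates the protocol's methods. SAP Section 6 lists what is not done because of early termination, namely healthcare resource utilisation and the SPECT analysis. The supportive Cox model is not on that list.

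**The concern.** A sensitivity analysis of a non-inferiority result has to return the same quantity as the primary analysis, a treatment hazard ratio with a bound to set against the margin. If treatment is a candidate for selection, the final model may not contain it.

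The selection test also asks the wrong question. Entry depends on evidence that the hazard ratio differs from 1, while the margin is fixed elsewhere: "The NI margin to be used for the analyses summarized in Sections 12.5.2 and 12.6.1 will be 1.20". A trial in which the arms do equally well supports non-inferiority, yet gives selection no reason to enter treatment. When treatment does enter, the estimate has passed a significance filter and its reported standard error ignores that.

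LVEF, NYHA class and natriuretic peptide are the factors the protocol's background names as adjusted for in the earlier imaging study. Randomisation is stratified by centre only (Protocol 6.2, SAP 2.5), so these factors are balanced by chance alone. As the two documents stand, it is unclear whether any adjusted estimate will be produced.

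**Working it through.** **Inputs.** From Protocol 12.8: "Alpha = 0.025, 1-sided"; power 80%; "1:1 randomisation to AdreView™ and SoC groups"; "Assumed HR: 0.84"; 247 events; 2001 patients; 36-month mortality 11.34% (AdreView) and 13.33% (SoC). The margin of 1.20 is from 12.9. The entry p-values below are assumptions (two-sided), because the documents give none.

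**Reproducing the plan's figures.** Schoenfeld events = 4 × (1.960 + 0.842)² / [ln(0.84/1.20)]² = 4 × 7.849 / 0.1272 = 246.8, which rounds up to 247. Dividing 246.8 by the mean mortality (0.1134 + 0.1333)/2 = 0.12335 gives 2001. The plan's design figures are therefore a sound basis for what follows.

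**Probability that treatment is left out.** With 247 events and equal allocation, the standard error of the log hazard ratio is 2/√247 = 0.1273. At a true hazard ratio of 0.84 the expected z is ln(1/0.84)/0.1273 = 0.1744/0.1273 = 1.37. With critical value c, treatment is left out with probability Φ(c − 1.37) − Φ(−c − 1.37). For c = 1.96 this is Φ(0.59) − Φ(−3.33) = 0.72.

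**Non-inferiority met, but no treatment effect in the supportive model.** Non-inferiority is met when the estimated log hazard ratio is below ln 1.20 − 1.96 × 0.1273 = −0.067, that is, an estimate below 0.935. At entry p 0.05, treatment enters on the favourable side only if the estimate is below exp(−1.96 × 0.1273) = 0.779. Estimates between 0.779 and 0.935 meet non-inferiority and leave treatment out.

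| Assumed entry p | Left out, true HR 0.84 | Left out, true HR 1.00 | Estimate needed to enter (favourable side) | NI met and treatment left out, true HR 0.84 |
|---|---|---|---|---|
| 0.05 | 72% | 95% | below 0.779 | 52% |
| 0.15 | 53% | 85% | below 0.833 | 33% |
| 0.25 | 41% | 75% | below 0.864 | 21% |

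At entry p 0.05 the supportive model could therefore corroborate superiority but hardly ever plain non-inferiority.

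**Check by simulation.** Forward selection was run in 600 simulated trials of 2001 patients and 247 events, using an unstratified Cox model with assumed covariate hazard ratios per SD of 1.3, 1.3 and 1.6. At a true hazard ratio of 0.84 and entry p 0.05, treatment was left out in 73%. Non-inferiority was met without treatment in the model in 52%.

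**Fewer events.** The study stopped early and the documents give no event count. At 0.84 and entry p 0.05, treatment would be left out in 81% of trials with 150 events, 86% with 100 and 91% with 50. These counts are illustrative.

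**What fixed adjustment gains.** In the same 600 trials, forcing in treatment and all three covariates gave non-inferiority power of 81%, against 79% unadjusted. The Monte Carlo standard error of each figure is about √(0.8 × 0.2/600) = 1.6 points. The covariate strengths are not in the documents. The table in 12.8 allows a rough check for LVEF alone. Mortality is 0.79 × 20.25 + 0.21 × 9.72 = 18.0% at LVEF 25–30% and 0.75 × 15.14 + 0.25 × 4.68 = 12.5% at 30–35%. The hazard ratio is ln(1 − 0.180)/ln(1 − 0.125) ≈ 1.49, and with the assumed 1:4 mix the log-hazard SD is ln(1.49) × √(0.2 × 0.8) ≈ 0.16. That is weak on its own. The documents give no comparable figures for NYHA class or natriuretic peptide.

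**The case against.** The strongest reply is that *initial covariates* may mean the starting model. All four terms would then be in from the outset and pure forward selection would drop none of them. That reading is open, and the percentages above do not apply to it. But the sentence also says stepwise, and a stepwise procedure can remove terms at a stay threshold that is likewise not stated. The text supports neither reading firmly enough to program from.

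Four stronger readings are tempting and should be resisted.

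- **That the SAP removed the analysis on purpose.** The documents do not show a decision. The SAP is silent, Section 6 does not list the analysis, and Section 1 says the SAP elaborates the protocol. Its status is unresolved.
- **That the baselines are never used.** LVEF and NYHA class define eligibility (Protocol 7.2 and 7.3), natriuretic peptide is summarised by arm (SAP 5.5.3), and the exploratory analyses are redacted. Only visible efficacy models can be judged.
- **That adjustment would rescue power or correct a biased hazard ratio.** The gain is about two points under assumed prognostic strength, and SAP 5.4.4 already accepts that the sample is too small for hierarchical testing. In a separate simulation of 800 trials, with an assumed prognostic SD of 1.0 on the log-hazard scale, the mean hazard ratio moved from 0.848 to 0.839 on adjustment. That is the usual difference between a marginal and a conditional Cox estimate; it does not show that the primary analysis is wrong.
- **That raw BNP and NT-proBNP values are pooled on one scale.** The text gives no combination rule at all, so this is under-specification and not a stated error.

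It is also fair to say that the primary hazard ratio and its bound against 1.20 are estimated whatever happens here.

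**Conclusion.** The point holds in a limited form. The only covariate-adjusted analysis of mortality in the visible text does not guarantee a treatment hazard ratio, and the SAP omits it without explanation. No visible efficacy model therefore adjusts for LVEF, NYHA class or natriuretic peptide.

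If treatment is a candidate term, omission at the design values runs from 41% to 72%, depending on an entry threshold that the plan does not state. If all terms start in the model, the risk comes only from stepwise removal. The figures for fewer events are illustrative, and they matter only if the protocol's model is still to be run.

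The primary analysis, the one-sided 0.025 level, the 247 events and the non-inferiority conclusion are not affected. This is a change worth making because it is cheap and settles a disagreement between the two documents.

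**What to change.** Replace the stepwise sentence and add one paragraph to SAP 5.4.2, before the sign-off that SAP Section 1 places ahead of database lock:

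- A supportive Cox model for all-cause mortality, stratified by country as in the primary analysis, with study arm always in the model and LVEF, NYHA class and log natriuretic peptide as fixed covariates. No selection.
- Natriuretic peptide standardised within assay, using the mean and SD of the log values with both arms combined.
- The adjusted hazard ratio and its confidence interval reported against 1.20 and labelled as a conditional hazard ratio, so that a difference from the primary estimate is not over-read.
- A rule for a missing natriuretic peptide that agrees with Protocol 12.11 and the no-substitution rule in SAP Section 5. Complete cases with the number excluded would do. A separate missing category would also do, if the peptide is entered in within-assay categories.

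The departure from Protocol 12.5.4 should be recorded under Protocol 12.13. If the sponsor prefers not to run an adjusted model, the SAP should say so, give the reason, and report that as the deviation instead.

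The cost is one paragraph, one extra model and possibly a few excluded patients. The event target and the sample size do not change.
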